1.24. Expected adverse events

1.24.1. Potential adverse events related to RSV infection

We would expect subjects to experience typical symptoms of a common cold (including, but not limited to: fever, headache, malaise, rhinorrhoea, nasal congestion, sneezing, sore throat, and cough). These would not be deemed adverse events, unless in the opinion of the study doctor. However, fever greater than 38°C for more than three consecutive days or withdrawal from the study due to intolerable symptoms in more than two subjects in any arm will lead to a suspension of the study. The safety monitoring committee will be convened to determine any systematic cause for unexpectedly severe symptoms.

Any illness resulting in

- **Sustained elevated heart rate >120bpm AND**
- **Sustained low blood pressure SBP<100**
- **Sustained elevated respiratory rate >30/min AND**
- **Sustained low blood oxygen SaO₂<94%**
- **Evidence of pneumonia on clinical examination**

will lead to referral for assessment in Accident and Emergency. Hospitalisation of any subject will lead to immediate suspension of the trial. The safety monitoring committee will be convened to assess the clinical evidence to determine whether the study may proceed.

1.24.2. Potential adverse events of bronchoscopy

Bronchoscopy is a safe procedure, with serious complications occurring in less than 1 in 1000 procedures. It is frequently performed on patients with lung diseases such as asthma, and even in critically-ill and frail elderly patients. The bronchoscopy may cause cough for a few hours, and there may be some discomfort during the procedure, but this is reduced with local anaesthetic and sedation.. The sedation makes participants drowsy, but this usually wears off after a few hours. Participants should not drink alcohol after receiving sedation. Minor bleeding caused by irritation of the airways from the telescope may occur (less than 1 in 100), but this does not require treatment. Serious bleeding requiring treatment is very rare (less than 1 in 1000). The fluid used to wash the airways (lavage) can cause some irritation, which manifests as a brief fever in 10-30% of cases. This is self-limiting and can be treated with paracetamol. On rare occasions the airways can narrow – if this occurs medication can be given to open the airways. Occasionally after taking the tissue sample (biopsy) people can cough up small amounts of blood but this will stop without further treatment. Very rarely (less than 1 in 1000), the lung can collapse (pneumothorax) after bronchial biopsy; we would arrange for all necessary treatment in the unlikely event should this occur.

Bronchosorption is likely to have less adverse effects than bronchoalveolar lavage, brushing and biopsy (the standard bronchoscopy tools) as it should not cause bleeding, infection or a reactive pyrexia. The only additional adverse event relating specifically to bronchosorption is dislodgement of the SAM from the forceps. If this does occur the SAM can be retrieved using standard endobronchial forceps and snares available routinely in the bronchoscopy suite.

1.23.3 Potential adverse effects of chest X-ray

Volunteers participating in this study will receive one chest Xray, which is entirely for research purposes. The estimated dose will be 0.014mSv (national Diagnostic Reference Level), which is approximately equivalent to 2.5 days natural background radiation and carries risk of inducing a

cancer of approximately 1:1000,000 based on risk factors for a healthy adult. This is classified as a trivial risk level (ICRP 62).

1.25. Reporting procedures

All adverse events should be reported. Depending on the nature of the event the reporting procedures below should be followed. Any questions concerning adverse event reporting should be directed to the Chief Investigator in the first instance.

A Safety Monitoring Committee (SMC) will be established to advise the trial team on study progression in the event of a safety concern. The SMC will be informed of all unexpected AEs at least monthly during the clinical study period and convene during the study if there are any serious adverse events, protocol deviations, or other safety issues. The SMC will be appointed and meet once (in person or by teleconference) prior to commencement of the study. The committee will consist of at least three members independent of the study team experienced in clinical trials and experimental medicine, with at least one member familiar with human challenge studies and one member experienced in respiratory infections. If any pausing rules or other safety issues arise, they will be convened to assess the clinical data and make a judgment on whether the study can proceed.

1.25.1. Non serious AEs

All such events, whether expected or not, should be recorded. These will be discussed monthly by the safety monitoring committee (see Section 12)

1.25.2. Serious AEs

An SAE form should be completed and faxed to the Chief Investigator and the Sponsor within 24 hours. The safety monitoring committee (see Section 12) will also be informed and a meeting convened as soon as possible.

All SAEs should be reported to the West London REC 2 Research Ethics Committee where in the opinion of the Chief Investigator, the event was:

- 'related', i.e. resulted from the administration of any of the research procedures; and
- 'unexpected', i.e. an event that is not listed in the protocol as an expected occurrence

Reports of related and unexpected SAEs should be submitted to ethics, the sponsor and the R&D office within 15 days of the Chief Investigator becoming aware of the event, using the NRES SAE form for non-IMP studies.

Contact details for reporting SAEs

[contact]

[contact] for the attention of [name] and/or [name]
[contact]

Please send SAE forms to: Section of Infectious Disease, [name], Imperial College London, Hammersmith Campus, [name]
[contact](Mon to Fri 09.00 – 17.00)

ASSESSMENT AND FOLLOW-UP

Study participants will be seen frequently during the study period, and at least daily for 10 days following infection. They have details to contact the study doctor and research nurses and will be offered daily telephone contact. In this way participants will be assessed regularly by the investigating team and any adverse events detected rapidly; subjects meeting the criteria for a serious adverse event will be offered prompt treatment as appropriate.

Subjects will have completed the study when they have had final convalescence investigations, expected to be 180 days after initial inoculation with the RSV virus. The overall study will be completed when sufficient numbers of subjects have been recruited. The end of the study is defined as the last visit of the last participant.

When the study is completed they will not be routinely followed-up. If a participant loses capacity during the study, then the participant would be withdrawn from the study. Identifiable data or tissue already collected with consent would be retained and used in the study. No further data or tissue would be collected or any other research procedures carried out on or in relation to the participant. Subjects will return to the care of their GP following completion of the study. Those who have experienced an SAE will be followed up until resolution of the SAE or until it is deemed by the CI or clinician in charge of the participant's clinical care that no further follow-up is required.

The study is a low-risk non-CTIMP, carried out by an experienced CI and study team. The study has appropriate risk assessments in place and will be checked through the PRB system at ICRF. Local monitoring will be carried out by study staff to ensure that CRFs are being completed, with no key data missing.

STATISTICS AND DATA ANALYSIS

Based on pilot data from Cherukuri et al., we calculate that a sample size of 8 in each arm would be sufficient to find a difference of 267 SFU/10⁶ between RSV-specific interferon- γ T cell counts by ELISpot in blood, with 80% power using a 2-sided unpaired t-test with 5% significance level (where the variability in each group is 130). Previous data from de Bree et al. studied epitope-specific T cells detected by tetramer that was normally distributed with standard deviation 0.0338. If the true difference in the experimental and control means is 0.0528 as their data indicated, we would need to study 8 experimental subjects and 8 control subjects to be able to reject the null hypothesis with a type I error probability of 0.05. However, tetramer technology (which we are using to mark RSV-specific T cells) depends on matching of certain cell surface markers known as Human Leukocyte Antigen (HLA). Only a proportion of the population have each type of HLA, so not all participants will be suitable for tracking with all tetramers. We therefore aim to recruit 32 volunteers to each group in order to obtain at least 8 individuals with each HLA type required for tetramer labelling. T cell numbers will be compared between young and elderly cohorts using an unpaired t-test (if normality of the T cell distribution, or its transformation, is satisfactory as assessed by histogram with q-qplot and Shapiro-Wilks test) or a Mann-Whitney test (if normality is not satisfactory).

We will perform gene expression analysis on each of 6 patients prior to inoculation and at 3 post-baseline time points. Our main analysis will identify differentially expressed genes between young and elderly adults at each post-baseline time point. The sample size, calculated using the size package from bioconductor which provides pilot data of gene expression variability from the U95 package, predicts that 6 individuals in each group will give us 80% power to detect a potential fold change of 3 in up to 67% of the genes with a Bonferroni multiple testing correction with a genome-wide 5% significance level.

Quantitative assessments of symptom scores, lung function, virus load, leukocyte numbers and inflammatory markers will be compared within subjects to determine differences between baseline

and during infection. Intra-subject differences will be analysed using ANOVA and 2-tailed paired Student's t-tests or Wilcoxon signed rank test as appropriate. Correlations between inflammatory cell, illness severity, viral load and leukocyte counts will be examined using Spearman's rank correlations to investigate possible causal relationships.

Data and all appropriate documentation will be stored for a minimum of 10 years after the completion of the study, including the follow-up period according to Imperial College London policy.

REGULATORY ISSUES

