Chief Investigator: [name]

Co-investigators: [name]

Study Site

The study will take place at Hammersmith and St Mary's Hospitals, London – part of the Imperial College Healthcare NHS Trust.

Study Coordination Centre

For general queries, supply of study documentation, and collection of data, please contact:

Study Coordinator: [name]

Position: Professor of Infectious Diseases

Address: Section of Adult Infectious Disease, Imperial College London, Hammersmith Campus, [name]

[contact]

E-mail: [contact]

Clinical Queries

Clinical queries should be directed to [name] who will answer or direct the query to the appropriate person.

Sponsor

Imperial College London is the research sponsor for this study. For further information regarding the sponsorship conditions, please contact the Head of Research Governance and Integrity ([name]) at:

Head of Research Governance and Integrity [name]

[name]

[name]

[name]

[name]

[contact]

Funder

The Medical Research Council (MRC) has provided funding for this study, in conjunction with Glaxo Smith Kline (GSK). This protocol describes the above study and provides information about procedures for entering participants. Every care was taken in its drafting, but corrections or amendments may be necessary. These will be circulated to investigators in the study. Problems relating to this study should be referred, in the first instance, to the Chief Investigator.

This study will adhere to the principles outlined in the UK policy framework for health and social care research (Version 3.3, 01/11/17). It will be conducted in compliance with the protocol, the Data

Protection Act and other regulatory requirements as appropriate including Good Clinical Practice (GCP).

STUDY SUMMARY

TITLE	Adaptive immunity in older adults infected with respiratory syncytial virus
DESIGN	Human viral challenge study in healthy older volunteers
AIMS	
 1. To test the hypothesis that immune (especially T cell) responses to RSV are quantitatively and qualitatively impaired with aging 2. To identify the mechanisms underlying reduced antigen-specific cell-mediated immunity (CMI) to RSV by comparing the phenotypic and transcriptional changes in T-cells following experimental challenge with RSV in healthy older adults with young adult volunteers.
POPULATION	Healthy persons aged 18 to 40 years and 60 to 75 years. Up to 42 subjects in total

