Based on extensive preclinical and clinical research, we hypothesise that severe RSV disease (particularly in the setting of older age and pre-existing airways disease such as chronic obstructive pulmonary disease (COPD)) represents a dysregulated and over-exuberant inflammatory response to infection. Steroids have limited efficacy, and identification of druggable inflammatory pathways in severe RSV disease would be of great potential value. A number of promising clinical assets are ready for investigation, however, our ability to test novel therapeutics is limited by the currently available models of viral disease and clinical endpoints tied to disease processes. Observational studies of natural infection are constrained by sampling, timing and access. We therefore propose to extend the experimental human RSV infection studies established at Imperial College to investigate the pulmonary response to RSV infection in older adults, with the development of novel clinical endpoints which can then be used to evaluate the possible impact of treatment with validated novel anti-inflammatory agents in human RSV disease.

Safety of experimental human infections with RSV Since 2010, we have been conducting experimental human challenge studies in volunteers aged between 18 and 55. To date, 61 individuals have been inoculated safely, with around 55% subsequently developing PCR-confirmed infection. Of those, around 66% develop symptoms consistent with a common cold. The infections have been uniformly mild, self-limiting and there have been no serious adverse events.

Challenge studies overcome the many difficulties associated with studying a naturally infected patient group where diagnosis is often delayed; the timing and dose of inoculating virus is extremely variable;

many patients have underlying medical conditions influencing their immune responses; and where they may be subject to therapeutic measures that alter those responses. Using a well-characterised, fully virulent GMP-certified challenge strain of RSV will allow us to closely replicate natural infection but also provide us with the control required to answer important questions about the essential immune responses required for protection and which of these may be impaired with increasing age.

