1.8. Recruitment

Subjects will be recruited by advertisement in local newspapers, around College sites, the Surrey Clinical Research facility database, and online: the Imperial Trust website, Gumtree, Student Union websites, ICRF website, and on social media such as the Imperial CRF Twitter page. Additionally, respondents to adverts for prior research projects in the department will be contacted and invited to take part in our study (they have previously given their consent to be contacted). If interested, they will be invited for screening. The total number includes up to 20 in the pilot safety study. We aim to enrol up to 12 young non-smoking (18-40 year olds) and up to 30 older non-smoking (60-75 year olds) in the main study.

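### The tetramer comparison is sized on 32 recruits per age group, but enrolment is capped at 12 young and 30 older, so the stated sample size is wrong as written, chiefly for the young group

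*Combined protocol and SAP*

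**What the plan says.** The Statistics and Data Analysis section sizes two T-cell comparisons between young and older participants.

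- **ELISpot.** A difference of 267 SFU per million cells with variability 130 leads to 8 per arm, "with 80% power using a 2-sided unpaired t-test with 5% significance level".
- **Tetramer.** The outcome is taken as "normally distributed with standard deviation 0.0338". The section continues "If the true difference in the experimental and control means is 0.0528 as their data indicated", and concludes that 8 subjects per group are needed to "reject the null hypothesis with a type I error probability of 0.05". It gives no power and no sidedness for this test.

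Tetramers work only in people with the matching HLA type, so the section then inflates the 8: "We therefore aim to recruit 32 volunteers to each group in order to obtain at least 8 individuals with each HLA type". No HLA type is named and no frequency is given.

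Section 1.8 (Recruitment) says: "We aim to enrol up to 12 young non-smoking (18-40 year olds) and up to 30 older non-smoking (60-75 year olds". It adds that the total includes up to 20 pilot participants. The Study Summary gives the population as "Up to 42 subjects in total".

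**The concern.** Two current statements of the study's size disagree. The sample-size text needs 32 + 32 = 64 participants, and the recruitment text allows 12 + 30 = 42. The 32 exists only to produce 8 HLA-matched people per group, so a smaller group feeds straight through to the number available for the test.

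Whether T-cell responses are impaired with age is the first aim in the Study Summary, and the tetramer assay is one of two T-cell comparisons with a sample-size calculation. If the text stays as it is, a non-significant tetramer result could be read as coming from 8 v 8 matched participants when far fewer young participants contributed.

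**Working it through.** **Inputs.** From Statistics and Data Analysis: difference 0.0528, SD 0.0338, type I error 0.05, 8 matched per group, 32 recruited per group. From section 1.8 and the Study Summary: at most 12 young, 30 older, 42 in total. Assumed: a two-sided test with an 80% power target, as stated for the ELISpot, because the tetramer sentence gives neither.

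**Step 1: reproduce the 8.** The standardised difference is 0.0528/0.0338 = 1.562. For an unpaired t-test with n1 and n2 subjects, the noncentrality is 1.562/√(1/n1 + 1/n2) on n1 + n2 − 2 degrees of freedom. At 8 v 8 it is 1.562/0.5 = 3.12 on 14 df, giving 82.7% power. At 7 v 7 power is 76.5%. Eight per group is therefore the smallest number reaching 80%, and the plan's figure reproduces.

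**Step 2: reproduce the 32.** 32 = 8/0.25. The inflation works only as an expectation at a 25% HLA frequency, which is implied and not stated.

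**Step 3: compare with the caps.** 12 + 30 = 42, which equals the Study Summary total, so the pilot participants are inside it. The pilot groups in section 1.6 (2 + 3 + 2 + 3 + 5 + 5 = 20) are all aged 60 to 75, so the pilot adds no young participants on any reading. The young cap is 12/32 = 37.5% of the target and the older cap is 30/32 = 94%. Screening and eligibility (sections 1.9 to 1.11) include no HLA typing or selection that could enrich the 12.

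**Step 4: matched numbers and power under the caps.** Let p be the HLA frequency. Matched counts are Binomial(12, p) and Binomial(30, p). Mean power is the sum over i and j of P(i matched young) × P(j matched older) × power(i, j), taken as zero where no t-test is possible.

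| p | Expected matched, young / older | P(at least 8 of 12 young) | P(at least 8 of 30 older) | Mean power at 12 v 30 |
|---|---|---|---|---|
| 20% | 2.4 / 6 | 0.06% | 24% | 37% |
| 25% | 3 / 7.5 | 0.3% | 49% | 48% |
| 30% | 3.6 / 9 | 1% | 72% | 57% |
| 40% | 4.8 / 12 | 5.7% | 96% | 73% |
| 50% | 6 / 15 | 19% | 99.7% | 84% |

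As a check at p = 25%: 3 v 7 has noncentrality 1.562/√(1/3 + 1/7) = 2.26 on 8 df and power 51%; 3 v 8 gives 54%.

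Expecting 8 matched among 12 young needs p = 8/12 = 67%, and an 80% chance of at least 8 needs about 73%. Older participants cannot readily make up for missing young ones. For 80% power, 5 matched young need 14 matched older and 4 need 26. With 3, no number up to 299 (the limit searched) is enough.

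**Step 5: the ELISpot under the same caps.** Reading the variability of 130 as an SD, 267/130 = 2.054. At 12 v 30 the noncentrality is 2.054/√(1/12 + 1/30) = 6.01 on 40 df, and power exceeds 99%. At 12 v 30, 80% power covers a difference of 0.98 SD, so 267 SFU would still have 80% power with an SD as large as 267/0.98, about 272.

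**The case against.** The contradiction in numbers stands, but several stronger readings are tempting and the documents do not support them.

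- **That a promised tetramer power cannot be delivered.** The plan states no power for this test. The 83% at 8 v 8 is a back-calculation, and the power at 12 v 30 depends on a frequency that the plan does not give. At 50% frequency, mean power is 84%, as good as 8 v 8. Only 32 per group is strictly out of reach. Eight matched young participants are very unlikely at 25% and unlikely even at 50%.
- **That only infected participants count.** Section 1.1 reports "around 55% subsequently developing PCR-confirmed infection" in earlier challenge studies. Applying 55% to a 25% HLA frequency would lower mean power to about 22%. But the statistics section does not restrict the comparison to infected people, and Table 1 schedules PBMC samples before inoculation, so a baseline age comparison is possible. The 22% describes an analysis that the plan does not specify.
- **That even 32 per group would fail.** At 25% frequency, at least 8 matched arise with probability 57% in one group and 32% in both (0.568² = 0.32). But narrowly missing 8 costs little: 32 v 32 still averages about 78% power. This is a point about the words at least, not a second defect.
- **That the T-cell age comparison as a whole is lost.** The ELISpot needs no HLA match and remains well powered.

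It is also fair to say that section 1.5 lists the comparison with young adults as exploratory, and that having 30 older participants in place of 32 changes little.

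**Conclusion.** The tetramer sample-size statement is wrong as written. It rests on 32 recruits per age group while enrolment is capped at 12 young and 30 older, and the shortfall is almost wholly in the young group. That conclusion needs no assumption.

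The size of the consequence does. It rests on the planned difference and SD, a two-sided 5% test carried over from the ELISpot, no HLA selection, and an HLA frequency that the plan must supply. At the implied 25%, the test at 12 v 30 has roughly even odds of detecting the planned difference. It approaches the 8 v 8 benchmark only for a type carried by about half of people.

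This should be fixed, but it is not critical: the comparison is exploratory, the primary safety objective is untouched, and the other sized T-cell comparison holds up.

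**What to change.** In Statistics and Data Analysis:

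1. Replace the 32 per group with the actual caps of 12 and 30, so that it agrees with the Study Summary and section 1.8.
2. Name the HLA types to be used and the frequency assumed for each.
3. Withdraw, for the young group, the statement that at least 8 individuals of each type will be obtained.
4. Restate the tetramer power per HLA type at 12 v 30 under those frequencies, with sidedness and target power given.
5. State that the ELISpot is the adequately powered T-cell comparison between age groups, and that the tetramer comparison is descriptive unless the restated power supports a test. Confirm there that the ELISpot variability of 130 is an SD.

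A single model pooling all tetramers, with one age-group effect, is an option but not a requirement. It would let every participant with at least one matched type contribute. It assumes the same age effect for every epitope, and its gain cannot be judged until the tetramers are named.

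The cost is wording and a less favourable stated power for the tetramer comparison. No extra participants are needed.

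### The young-versus-older tetramer comparison has no HLA or epitope term; at the enrolment cap a test per HLA type has about 3 v 7-8 people and 51-54% power, and an HLA-stratified summary model could regain part of this

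*Combined protocol and SAP*

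**What the plan says.** The unnumbered section on statistics and data analysis sizes the tetramer comparison from published data: T cells "detected by tetramer that was normally distributed with standard deviation 0.0338". It continues "If the true difference in the experimental and control means is 0.0528", then "we would need to study 8 experimental subjects and 8 control subjects", "with a type I error probability of 0.05". Power and sidedness are not given for this calculation. The neighbouring ELISpot calculation is stated "with 80% power using a 2-sided unpaired t-test with 5% significance level".

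The section then notes that tetramers depend on HLA type, "so not all participants will be suitable for tracking with all tetramers", and raises the recruitment target to 32 per group so that each required HLA type has at least 8 people. The analysis sentence follows: "T cell numbers will be compared between young and elderly cohorts using an unpaired t-test" if normality is satisfactory, possibly after transformation, and otherwise a Mann-Whitney test.

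Nothing says whether each HLA type is tested alone or all are combined, or how a person with two matching types is handled. The number of tetramers, their carriage rates and their overlap are not given.

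Section 1.8 (Recruitment) sets enrolment at "up to 12 young non-smoking (18-40 year olds) and up to 30 older non-smoking (60-75 year olds". The Study Summary gives up to 42 in total.

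**The concern.** Several tetramers, each read in a different and possibly overlapping subset, do not form one two-sample problem. The stated test can be applied in two ways, and the plan does not choose.

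- **One test per HLA type.** Each uses only the carriers of that type, so the young group becomes very small. Several tests are run with no rule for reading them together.
- **One test over all types.** Epitopes with different typical frequencies are mixed, which adds noise. The age groups are not randomised and nothing balances HLA type between them, so a difference in HLA mix could appear as an age difference. A person with two types would also be counted twice.

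Both aims in the Study Summary concern age-related change in T cell immunity, and the tetramer comparison is what raises the recruitment target from 8 to 32. If the choice is left until results are seen, it becomes avoidable flexibility.

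**Working it through.** **Inputs from the documents.** Difference 0.0528; SD 0.0338; alpha 0.05; 8 v 8 required; 32 per group to get 8 per type; enrolment up to 12 young and 30 older. Two-sided testing and 80% power are taken from the ELISpot sentence.

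**1. The plan's figure.** Standardised difference d = 0.0528/0.0338 = 1.562. Noncentral t with noncentrality d × √(n1·n2/(n1+n2)) and n1+n2−2 degrees of freedom:
- 7 v 7: 76.5% power.
- 8 v 8: noncentrality 1.562 × 2 = 3.12, 14 df, about 83% power.

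So 8 per group is the smallest number that reaches 80%, and the plan's figure reproduces.

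**2. Carriers per type.** Implied carriage is 8/32 = 25%. Expected carriers are 12 × 0.25 = 3 young and 30 × 0.25 = 7.5 older. By the binomial, the chance of at least 8 young carriers among 12 is 0.3% (57% even among 32). The chance of 0 or 1 is 16%.

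**3. Power of one test per type.**
- 3 v 7: noncentrality 1.562 × √(21/10) = 2.26, 8 df, 51%.
- 3 v 8: noncentrality 1.562 × √(24/11) = 2.31, 9 df, 54%.

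Averaged over random carrier numbers it is about 44-48%; the lower end counts a trial with fewer than two carriers in either group as a failure. Averaged power over a range of assumed carriage (upper convention):

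| Carriage | 15% | 20% | 25% | 30% | 40% | 50% |
|---|---|---|---|---|---|---|
| Power | 25% | 37% | 48% | 57% | 73% | 84% |

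**4. HLA-stratified model.** One common age effect and one intercept per type. The number of types and their overlap are assumptions.
- No overlap, K types, n1+n2−K−1 df: two types (6 v 15) 86%; three types (9 v 22.5) 97%.
- Independent 25% carriage (simulated): two types about 75% with one value per person, up to 78% with all values; three types 85-86% and 90-91% respectively. The all-values figures assume a within-person correlation of 0.5.
- Half the effect, one value per person: 28% with two types, 34% with three.
- Only one epitope of three affected: 17-18% for the common estimate, against 45% for that epitope's own test.

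**5. Pooled t-test (simulated, three types, one value per person).** Power is 89% if epitope means are equal. It is 74%, 51% and 36% if the SD between epitope means is 1, 2 or 3 within-group SDs. The stratified model stays at 85-86% throughout, so with equal means pooling is slightly better.

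With no age effect, epitope means 1 SD apart and assumed carriage of 45/25/25% in one age group v 25/25/45% in the other, the pooled test rejects in 15-19% of trials and the stratified test in 4-5%.

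**The case against.** The strongest reply is that the power loss comes from enrolment, not from the t-test: with 8 v 8 carriers the plan's own test has 83% power. That stands. The conflict between 32 per group and 12 + 30 is the root cause, and a new model does not resolve it.

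Second, aiming for at least 8 people of each HLA type suggests per-type testing. A reader might infer that the plan pools epitopes; it does not say so, and the pooled figures describe only one reading of its silence. They also rest on assumed epitope means and HLA mixes.

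Third, a reader might infer that stratification simply restores the planned power or uses every participant. Neither is supported. The gain needs several tetramers with a similar standardised age effect. If only one epitope is affected, the common estimate does worse than that epitope's own test. With three independent types at 25%, 0.75³ = 42% of people carry none, about 5 of the 12 young adults. Only about 16% carry two or more (roughly 2 young and 5 older), so a participant variance would be poorly estimated.

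Fourth, safety is the primary objective (1.3) and the comparison with young adults is exploratory (1.5), so multiplicity across tetramers is tolerable if reported as such. The ELISpot calculation is not described as HLA-dependent and is untouched by this point.

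What remains is that the named test cannot represent the data structure described in the same paragraph, and that the choice between its two uses is left open.

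**Conclusion.** The point holds for the tetramer data, in conditional form. At the 25% carriage implied by the plan and the 12 + 30 cap, a per-type test has 51-54% power at the plan's own effect rather than about 83%. A pooled test avoids the small numbers but mixes epitopes and is open to confounding by HLA mix.

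An HLA-stratified summary is the better-specified comparison. Its power is about 75-78% with two overlapping types, short of 80%, and 85-91% with three. Both ranges assume independent 25% carriage and a similar standardised age effect of 1.56 SD in every epitope. The documents give neither the number of types nor any basis for a common effect. With one type there is no gain, and with one affected epitope little or none.

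It would go too far to conclude that the model fully recovers the planned power, or that the whole study was sized on this one comparison: ELISpot and gene expression are sized alongside it.

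**What to change.** For the tetramer data only, state in the statistics section:

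- The summary age comparison is one model of tetramer-positive T cells on age group, with epitope/HLA type as a fixed effect and participant as a random effect. If few people carry two types, use one value per person, chosen by a rule fixed in advance.
- The scale, raw or transformed, is chosen by the normality check already in the plan. If a rank test is needed, use van Elteren stratified by HLA type with one value per person.
- Report the age estimate with a 95% CI. Keep the per-epitope estimates and add an age-by-epitope check, because the summary relies on a common effect and can hide an effect confined to one epitope.
- List the tetramers and HLA types, with expected carriage and overlap.

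Separately, reconcile the target of 32 per group with the enrolment of 12 + 30 in the Study Summary and section 1.8, and restate the power per HLA type at the number that stands.

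The analysis change costs wording only and relies on the HLA matching that tetramers already require. Its downside is the common-effect assumption.
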